2.1 Overall objective and hypothesis: Our overall objective is to *innovatively use a dose-finding approach* to identify the recommended reimbursement amount for women with breast cancer enrolled in a clinical trial. We *hypothesize* that optimal reimbursement for trial-related expenses will decrease patient financial toxicity and increase trial retention. The *rationale* is that understanding the impact of reimbursement for trial-related costs will aid in addressing socioeconomic barriers to trial participation, thus allowing for more diversity in trial enrollment and ensuring equitable efficacy of cancer treatments when used in real-world clinical settings.

2.2 Specific aims: To accomplish this overall objective, we will propose the following specific aims:

Aim 1. Identify the recommended reimbursement amount in trial-enrolled women with breast cancer experiencing financial toxicity. We propose a pilot reimbursement dose de-escalation trial (continual reassessment method design; N=30) testing a monthly reimbursement for trial-enrolled patients who screen positive for financial toxicity. We will oversample patients who are Black (50%) or residing in rural locations (50%). Monthly patient-reported financial toxicity and reimbursement acceptability and appropriateness will be captured. Reimbursement dose will start at \$1000 and de-escalate if patients find the reimbursement dose suitable (negative financial toxicity screen, reimbursement dose deemed acceptable/appropriate).

Aim 2. Explore patient perceptions of trial reimbursement amounts. Using semi-structured interviews, we will explore the effects of reimbursement on (1) specific covered and uncovered trial-related costs, (2) financial toxicity, and (3) current retention and future participation in clinical trials.

4. Investigation Plan and Study Procedures

4.1 Study design and population: This will be a prospective, health services research study modeled after a traditional, dose de-escalation phase I trial design. The study population will include women with early stage breast cancer currently enrolled in the Investigation of Serial studies to Predict Your Therapeutic Response with Imaging and Molecular AnaLysis (I-SPY TRIAL 2) or metastatic breast cancer enrolled in any clinical trial at the UAB Medical Oncology Clinic.

4.2 Study duration: Two years.

4.3 Participants and recruitment:

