Dose number	Reimbursement dose amount	Decrease from starting dose in \$100 units	Prior probability of dose-limiting toxicity
1	\$1000	0.001	0.05
2	\$900	1	0.1
3	\$800	2	0.2
4	\$700	3	0.3
5	\$600	4	0.45
6	\$500	5	0.6

- 4.4.1.4 Dose-toxicity skeleton: Shown in **Table 1**.

As this is a dose de-escalation trial testing the feasibility of a dollar decrease in reimbursement from a maximum of \$1000, we are assessing the minimally tolerated dose. This refers to minimum dollar amount needed to alleviate trial-related financial toxicity for patients participating in I-SPY TRIAL2. With the data fitted to a logistic model, the minimally tolerated dose should be around

[figure not shown]
\$630 (i.e., a decrease of about \$370 from the starting dose of \$1000), and we would expect to detect it at the 5th dose (**Figure 1**).

Figure 1. Number and spacing of doses.

The operating characteristics also appear fine using a one-parameter logistic model (**Figure 2**).

Figure 2. Dose-toxicity scenarios.

4.4.1.5 Method of inference: We will use a Bayesian approach with informative priors.

4.4.1.6 Decision rules: We will choose the reimbursement dose with an estimated probability of a minimally acceptable, appropriate, and financial toxicity-limiting reimbursement dose closest to, but not greater than, the optimal reimbursement level.

4.4.1.7 Sample size and cohort size: Our total sample size for women with early stage breast cancer patients is 30, comprised of 6 cohorts of 5 patients

each. Our total sample size for women with metastatic breast cancer patients is also 30, comprised of 6 cohorts of 5 patients each.

4.4.1.8 Safety modifications: We expect minimal safety concerns with this study, since there is no medical/drug intervention.

4.4.1.9 Stopping rules: Early termination of phase I trials often occurs if adding additional patients to the trial will not result in changes to the identified optimal dose. As this is not a true phase I trial, but rather a health services pilot feasibility trial anchored within a phase I trial methodological design, no stopping will occur. Enrollment of our targeted 30 patients is necessary to understand our primary feasibility outcomes move our science forward to test outcomes in a larger randomized controlled trial.

[figure not shown]

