4.4.1.10 Patients will be dosed in cohorts of 5, with a maximum available sample size of 30 early stage and 30 metastatic breast cancer patients. The first cohort of 5 patients will be enrolled at the first reimbursement dose level of \$1000 per month for 4 months (\$4000 per patient in total). Patients will be surveyed biweekly to determine patient financial toxicity (COST tool¹⁹), acceptability of the reimbursement dose (Acceptability of Intervention Measure²⁰), and appropriateness of the reimbursement dose (Intervention Appropriateness Measure²⁰). Participants will be surveyed in-person at baseline, then biweekly over the phone. Semi-structured interviews will be completed in-person, with an option for completion virtually if the participant prefers. At the end of the 4-month period, reimbursement dose suitability will be determined as suitable by a cumulative negative financial toxicity screen and reimbursement dose deemed acceptable and appropriate in at least 4 patients (**Table 2**). If the reimbursement dose is found suitable (all of the 3 criteria are met in at least 4 patients), we will de-escalate the reimbursement dose for the next cohort of 5 patients (**Figure 3**). If the reimbursement dose is found unsuitable (at least 1 of the 3 criteria are not met in 2 patients), the next cohort of 5 patients will be enrolled at the same reimbursement amount (\$1000 per

Table 2. Reimbursement dose suitability and de-escalation criteria.

Reimbursement Dose Suitability Criteria	Instrument	Scoring	De-Escalation Criteria
Negative financial toxicity screen	Comprehensive Score for financial Toxicity (COST) ¹⁹	Scored 0-44, scores < 26 indicate financial toxicity	Average score ≥ 26
Reimbursement dose acceptable	Acceptability of Intervention Measure (AIM) ²⁰	4-item, 5-point Likert scale; higher scores indicate greater acceptability	Average score ≥ 4
Reimbursement dose appropriate	Intervention Appropriateness Measure (IAM) ²⁰	4-item, 5-point Likert scale; higher scores indicate greater appropriateness	Average score ≥ 4

month for 4 months). This sequence will continue until 30 patients have received the reimbursement intervention.

Figure 3. Study schema.

4.4.1.11 Justification of starting dose: The initial \$1,000 dose is based on a prior estimate of a logit model with $\beta_0 = -2.79$ and a slope $\beta_1 = 0.64$ for the dose in \$100 units. This was based on consensus among the investigators in the study and data from three studies:

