5.3 Secondary data analysis: To further understand potential cost and travel burdens to participate in a cancer clinical trial, we will abstract trial and patient data from UAB oncologic therapeutic trial treatment protocols and the OnCore database. Abstracted trial data will include factors associated with financial burden, such as visit frequency and sponsor payment to participants. Abstracted patient data will include sociodemographic and clinical characteristics, such as home address (to map distance/time required to travel to clinic).

6. Data and Safety Monitoring

- 6.1 Safety monitoring: [name] will be responsible for reviewing and monitoring all study data and any adverse events during data collection. The investigative team will meet with study personnel every 2 weeks to evaluate study progress, including

periodic assessments of data quality and timeliness, participant recruitment, participant risk versus benefit, and other factors that can affect study outcomes. Any unanticipated problems and adverse events will be reported to the UAB IRB according to policies. The risks involved for study participation are minimal and do not put safety at risk.

6.2 Data: Survey responses will be kept within an encrypted, password-protected database and stored in network drives with restricted access on a password protected computer. Data from this study housed at UAB will be destroyed within three years of study completion.

7. **Benefits**

The potential benefits include increased understanding of (1) the optimal reimbursement “dose” to reduce trial-related financial toxicity, (2) specific categories of trial-related expenses that could result in barriers to participation if not reimbursed, and (3) the impact of reimbursement on trial recruitment and retention outcomes. This understanding could benefit patients by reducing the trial-related financial toxicity in women with breast cancer, dismantling trial access barriers, and promoting greater diversity in trial samples.

8. **Potential Risks and Solutions**

- Concern: Reimbursement could be considered as undue influence for research participation.
- Solution: Reimbursement for trial-related expenses is considered a “just and fair,” non-coercive practice against patient exploitation by both the US Food and Drug Administration and American Society for Clinical Oncology.²⁴⁻²⁶ Coercion to participate in research is unlikely in our study since eligible women will have already enrolled in the I-SPY TRIAL 2.

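### Three passages plan 30 patients and three plan 30 per disease stage, and the target amount is defined for I-SPY 2 patients only; two parallel sequences are implied but not stated

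*Combined protocol and SAP*

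**What the plan says.** **Passages that describe 30 patients**

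- Section 2.2, Aim 1: a pilot trial with a "continual reassessment method design; N=30". The overall objective in 2.1 is singular: to "identify the recommended reimbursement amount for women with breast cancer enrolled in a clinical trial".
- Section 4.4.1.9, on why there is no early stopping: "Enrollment of our targeted 30 patients is necessary".
- Section 4.4.1.10, last sentence of the de-escalation rule: "This sequence will continue until 30 patients have received the reimbursement intervention".

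**Passages that describe 30 per stage**

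- Section 4.4.1.7 gives early-stage patients 30 places in 6 cohorts of 5, then adds: "Our total sample size for women with metastatic breast cancer patients is also 30", with the same cohort structure.
- Section 4.4.1.10, first sentence, sets the maximum at 30 early-stage and 30 metastatic patients.
- Section 5.1.1 repeats 30 of each. The total of 60 is not printed; it is the sum.

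**Population**

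- Sections 4.1 and 4.3.1 admit early-stage patients on I-SPY 2 and metastatic patients on any trial at the clinic.
- Section 4.4.1.4 defines the minimally tolerated dose as the least amount that relieves trial-related financial toxicity "for patients participating in I-SPY TRIAL2".
- Section 8, answering the undue-influence concern, says that "eligible women will have already enrolled in the I-SPY TRIAL 2".

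There is one skeleton (Table 1), one prior model (4.4.1.11), one expected amount (about $630), one first cohort and one rule for the next cohort. Section 5.1.3 plans comparisons by race and by residence, not by stage.

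**The concern.** In a continual reassessment design, the number of sequences is part of the algorithm. It decides whose data set the next cohort's amount, when enrolment ends, and how many recommended amounts the trial reports. The team needs to know this before assigning the second cohort. The plan gives two incompatible sample sizes, one of them attached to the sentence that ends the sequence.

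The target has a separate gap. Under 4.3.1 only early-stage patients enter through I-SPY 2, so the definition in 4.4.1.4 covers them and leaves out the metastatic patients, who are half of the 60. Nothing written says what amount the trial would be estimating for them.

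**Working it through.** **Inputs.** Cohort size 5 and 6 cohorts per stage (4.4.1.7); 4 months of observation per cohort and $1,000 per month at the starting level (4.4.1.10); two years' duration (4.2); target 40% (4.4.1.2); prior logit intercept -2.79 and slope 0.64 per $100 decrease (4.4.1.11).

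**1. The plan's own figures.** Per stage, 6 x 5 = 30, which agrees with 4.4.1.7. Both stages together make 2 x 30 = 60, which does not agree with the 30 of Aim 1 and 4.4.1.9.

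**2. The expected amount.** Setting -2.79 + 0.64x = ln(0.40/0.60) = -0.405 gives x = (2.79 - 0.405)/0.64 = 3.73. That is a decrease of about $373 and an amount of about $627, which agrees with the stated $370 and $630. The calculation yields one curve and one target amount; no second one is given for metastatic patients.

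**3. Maximum outlay.** Per patient, 4 x $1,000 = $4,000 if the amount never falls. For 30 patients this is 30 x $4,000 = $120,000. For 60 it is 60 x $4,000 = $240,000.

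**4. Minimum duration.** Each cohort is judged at the end of its 4 months before the next begins. The durations below assume no gap between cohorts and are therefore lower bounds.

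| Reading | Patients | Cohorts in series | Months | Amounts reported | Maximum outlay |
|---|---|---|---|---|---|
| Two parallel sequences, one per stage | 60 | 6 | 6 x 4 = 24 | 2 | $240,000 |
| One mixed sequence, ended at 30 | 30 | 6 | 24 | 1 | $120,000 |
| One mixed sequence of 60 | 60 | 12 | 12 x 4 = 48 | 1 | $240,000 |

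Of these, only the first gives 30 per stage within two years. The second cannot reach 30 in both stages. The documents give no accrual split. Assuming an even split, each stage would supply 15; if one stage supplied between one third and two thirds, it would supply 10 to 20. The third takes twice the stated duration and also contradicts the written end at 30.

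**5. Fit with the text.** The first reading agrees with 4.4.1.7, the opening of 4.4.1.10, 5.1.1 and 4.2. It agrees with the end of 4.4.1.10 only if 30 is read as 30 in each stage. It does not agree with N=30 in Aim 1, with the target of 30 in 4.4.1.9, or with the I-SPY 2-only definition in 4.4.1.4. No single reading fits every passage.

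**The case against.** The strongest reply is that the intent is clear enough. Section 4.4.1.7 gives each stage its own 6 cohorts of 5, which does not suit mixed cohorts. The paragraph that ends at 30 opens with 30 of each, so the closing 30 is most naturally per stage. The 24-month arithmetic matches the stated duration only on that reading. Figure 3, the study schema, is missing from the available text and may show two sequences.

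Most of this stands: two parallel sequences are probably meant, and it would be wrong to call the design wholly undetermined. But the reply works by inference, and it leaves Aim 1, 4.4.1.9 and the target definition in 4.4.1.4 uncorrected. A schema could settle the number of sequences, but it would not change those three passages.

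Section 8 is weaker evidence. Its I-SPY 2 sentence belongs to an argument about coercion and does not set eligibility, and the same section allows expansion to other breast cancer trials at the site. The sentence is still inaccurate for metastatic patients on other trials.

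A reader might go further and infer three things that the documents do not support:

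- **That the trial will in fact stop at 30 mixed patients.** This follows only if the two stages share one sequence, which no passage says.
- **That stage would be confounded with amount.** In a mixed sequence this needs the stage mix to drift over time; a constant mix would not produce it. No rule balances stage within cohorts, but nothing shows that drift is expected. Nor does the amount necessarily fall at each step, since it is held after an unsuitable cohort.
- **That the two groups are known to have different visit schedules and costs.** Only the I-SPY 2 schedule is described (section 8). A difference is plausible, but it is an assumption.

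**Conclusion.** The sample size, the end of the sequence and the target population are each stated in ways that conflict. Three passages give 30 patients and three give 30 per stage: a difference of 30 patients and $120,000 in maximum reimbursement. As written, the metastatic patients have no defined target amount. Two parallel stage-specific sequences are the implied design, but the available text does not state them.

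Applied to one mixed sequence, the written end point would stop enrolment at 30 in total. The planned 30 per stage could not be reached, and the single amount could not be attributed to either stage. That consequence is conditional on mixing.

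The contradictions in sample size and target rest on the text alone. The durations assume no gap between cohorts, the outlays assume no de-escalation, and the view on the number of sequences is subject to Figure 3. The point should be settled before the second cohort is assigned.

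**What to change.** Check Figure 3 first, then reconcile the text.

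1. In 2.2, 4.4.1.9 and the end of 4.4.1.10, state 30 per stage (60 in total), to agree with 4.4.1.7 and 5.1.1.
2. State that there are two parallel sequences, that cohorts do not mix stages, that each sequence ends at 30, and that each has its own model fit and recommended amount.
3. Extend the target definition in 4.4.1.4 to metastatic patients, and say whether the single skeleton and prior apply to both groups.
4. Correct the I-SPY 2-only sentence in section 8.
5. Confirm that the budget statement in 5.1.1, which justifies cohorts of 5 assuming no de-escalation, was worked out for 60 patients (at most $240,000) and not for 30 (at most $120,000).

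If one 30-patient sequence is intended, correct 4.4.1.7, the opening of 4.4.1.10 and 5.1.1 instead.

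The cost is protocol wording, a second model fit and a decision on whether the prior is shared. Under the two-sequence fix, no patients are added beyond those already in 4.4.1.7 and 5.1.1. The budget check may show a shortfall, which is better found now than midway through the sequences.

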4.3.1 Inclusion criteria: Participants will be women with early stage breast cancer currently enrolled in the Investigation of Serial studies to Predict Your Therapeutic Response with Imaging and Molecular AnaLysis (I-SPY TRIAL 2) or metastatic breast cancer enrolled in any clinical trial at the UAB Medical Oncology Clinic.

- 4.3.2 Exclusion criteria: Reasons for study exclusion include non-English speakers.
- 4.3.3 Sampling: Using standard-of-care patient-reported data collected in clinic, eligible patients will have screened positive for financial toxicity using the validated Comprehensive Score for financial Toxicity¹⁴ (COST; scored 0-44, scores < 26 indicate financial toxicity). Eligible patients will be approached during their clinic visit.
- 4.3.4 Informed consent: Informed consent will be obtained by a study coordinator through an informed consent form if the patient is interested.
- 4.4 Approach:
- 4.4.1 Aim 1: We will use the continual reassessment method phase I dose de-escalation clinical trial design under the assumption that financial toxicity may increase when the reimbursement “dose” decreases. Continual reassessment method is a model-based trial design that informs how the reimbursement “dosage” should be adapted for the next patient cohort based on past trial data.^{17, 18} The parameters to be used in the continual reassessment method are listed below.
- 4.4.1.1 Number of doses: We suspect six reimbursement dose amounts will be assessed. However, the number of dose amounts may decrease if a cohort finds their reimbursement dose amount as unsuitable (at least 1 of the 3 de-escalation criteria are not met in 2 patients), in which no dose de-escalation will occur in the next cohort.
- 4.4.1.2 Target toxicity level: The “toxicity” amount will be set at 40% (de-escalation criteria unmet in 2/5 patients) due to the low-risk nature of the “dose,” which is money rather than drug. Note that toxicity in this study is defined as suitability of the reimbursement dollar dose defined by 3 patient-reported measures: (1) financial toxicity (defined as out-of-pocket costs and accompanying psychological distress), (2) acceptability of the reimbursement dose, and (3) appropriateness of the reimbursement dose.
- 4.4.1.3 Dose-toxicity model: We will use a one-parameter logistic model.

Table 1. Dose toxicity skeleton.

[figure not shown]

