- 5.1.1 Sample size: A total of 30 women with early stage breast cancer and 30 women with metastatic breast cancer will be recruited for our study. We will oversample patients who are Black (50%) or residing in rural locations (50%) to ensure representation from patient groups routinely underrepresented in clinical trials. As this is a pilot data funding mechanism, it was necessary to balance both sample size and budgetary constraints. After accounting for research staff (research assistant, biostatistician) and study expenses (interview transcription, publication fees), cohort sizes of 5 were the maximum potential size assuming the potential of no de-escalation of the \$1,000 per month reimbursement constrained within a 2-year timeframe.
- 5.1.2 Power: Because this is a pilot study to assess feasibility of trial-related cost reimbursement to be used in a larger phase II trial, no true power calculation is required.²¹ Feasibility benchmarks will be defined as 80% retention of patients and retained patients completing at least 75% of bi-weekly surveys while enrolled.
- 5.1.3 Analysis: Descriptive sociodemographic, survey, and feasibility data will be calculated for all patients. Comparisons by race (white/black) and residence (rural/urban) will be investigated. Mean differences, or effect sizes, will be calculated using Cohen's d or Cramer's V to determine the magnitude of relationships in bivariate associations.²²

5.2 Aim 2 Analysis: Using a directed content analysis approach,²³ a codebook will be created as guidance. The initial codebook will be reviewed by [name] (*collaborator*, medical oncologist) and [name] (*collaborator*, health economist). Thematic analysis will be conducted by [name] (*PI*) and [name] (*research assistant*, disparities researcher) and used to qualitatively code interview text into codebook categories. Thematic concordance between [name] and [name] will be reviewed after every 2-3 interviews. If needed, new codes or subcodes will be created based on the data. Newly added codes will be used to create a final codebook. All interview transcripts will be reviewed using the final codebook. Themes by race and residence will be investigated.

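### The race and residence effect sizes in 5.1.3 are not adjusted for reimbursement amount or stage and carry no interval, so a mix that differs between amounts would shift them in either direction

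*Combined protocol and SAP*

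**What the plan says.** Section 5.1.3 opens with the data to be summarised: "Descriptive sociodemographic, survey, and feasibility data will be calculated for all patients". It then says "Comparisons by race (white/black) and residence (rural/urban) will be investigated" and gives the method: "Mean differences, or effect sizes, will be calculated using Cohen's d or Cramer's V to determine the magnitude of relationships in bivariate associations". It names no covariate, no stratification by amount, cohort or stage, and no confidence interval.

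Three other parts of the plan bear on this:

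- **Amount.** Section 4.4.1.10 assigns the amount by cohort. The first cohort receives $1000 per month. When at least 4 of 5 patients meet all three criteria, "we will de-escalate the reimbursement dose for the next cohort of 5 patients"; otherwise the amount is unchanged. Table 1 lists six amounts from $1000 to $500, but 4.4.1.1 adds: "However, the number of dose amounts may decrease if a cohort finds their reimbursement dose amount as unsuitable".
- **Expected effect of amount.** Table 1 gives prior unsuitability of 5%, 10%, 20%, 30%, 45% and 60%. Section 4.4.1.11 gives the logistic model behind it.
- **Sample.** Section 5.1.1 says: "A total of 30 women with early stage breast cancer and 30 women with metastatic breast cancer will be recruited for our study". It sets a 50% aim for Black patients and a 50% aim for rural patients, and mentions no balance across cohorts or amounts.

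**The concern.** Each patient's amount depends on when she enrols, and the design expects the amount to move the outcomes being compared. A bivariate contrast over all patients cannot separate the two if, say, Black or rural patients are more common in the later, lower-paid cohorts. The 50% aims could be met overall while the mix still changes along the sequence. Section 8 allows recruitment to widen to other breast cancer trials if accrual is low, which is one way the mix could change during the study.

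Stage raises the same question. Early-stage and metastatic patients each have six cohorts of 5, and 5.1.3 does not separate them. The two groups could sit at different amounts, and their race or residence mix could differ.

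At stake is how the comparisons are read. The background and preliminary studies make race and rural residence central to the rationale, and 4.4.1.11 says the suitability data will inform the next study. A crude gap that partly reflects who was paid what could be taken as a difference in need.

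**Working it through.** **1. The plan's own model.** Section 4.4.1.11: logit p = −2.79 + 0.64x, where x is the decrease from $1000 in $100 units. At the 40% target in 4.4.1.2, x = (logit 0.40 + 2.79)/0.64 = (−0.405 + 2.79)/0.64 = 3.73. The amount is then $1000 − $373 = $627. The plan says about $630, so its figure is reproduced.

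Model unsuitability at the six amounts is 0.058, 0.104, 0.181, 0.295, 0.443 and 0.601, close to Table 1.

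**2. Spurious gap, one cohort per amount.** Assumptions not in the documents: 15 Black and 15 White patients in one stage group of 30, no race effect at any amount, and the mixes below. With b_j Black patients in cohort j:

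gap = Σ b_j p_j / 15 − Σ (5 − b_j) p_j / 15

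For 1, 2, 2, 3, 3, 4:

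- Black: (0.058 + 0.208 + 0.362 + 0.885 + 1.329 + 2.404)/15 = 5.246/15 = 35.0%
- White: (0.232 + 0.312 + 0.543 + 0.590 + 0.886 + 0.601)/15 = 3.164/15 = 21.1%
- Gap 13.9 points. Cramer's V = 0.139 × 0.5 / √(0.280 × 0.720) = 0.155

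| Black patients per cohort | Gap (points) | V |
|---|---|---|
| even | 0 | 0 |
| 3, 2, 2, 2, 3, 3 | +3.5 | 0.04 |
| 1, 2, 2, 3, 3, 4 | +13.9 | 0.155 |
| 4, 3, 3, 2, 2, 1 | −13.9 | 0.155 |
| 0, 1, 2, 3, 4, 5 | +25.6 | 0.285 |
| 1, 2, 2, 3, 3, 4, all at $1000 | 0 | 0 |

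**3. The same mix under the stated rule.** One cohort per amount needs five de-escalations in a row. The probability that at most 1 of 5 patients is unsuitable is 0.970, 0.913, 0.776, 0.539 and 0.267 at $1000 to $600. The product is 0.10. The sixth cohort is at $500 with probability about 0.10, at $600 about 0.57 and at $700 about 0.32.

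Applying the 4.4.1.10 rule and the prior model to the mix 1, 2, 2, 3, 3, 4 (20,000 simulated sequences) gives a mean gap of 9.1 points. The 2.5th and 97.5th percentiles are 5.3 and 13.9. This range reflects which amounts are reached; it does not include sampling error in the outcomes.

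**4. Random mix.** If the 15 Black patients fall at random over the 30 places, with one cohort per amount, the gap due to amount averages 0 with SD 7.1 points. The sampling SE of the crude difference for 15 vs 15 is √(0.280 × 0.720 × 2/15) = 16.4 points. Chance imbalance in amount is therefore about 7.1²/16.4² = 0.19 of that variance: lost precision, not bias. For 30 vs 30 the SE is 11.6 points.

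**5. Precision of d.** Approximate 95% half-width: 1.96√(2/15) = 0.72 for 15 vs 15 (one stage), and 1.96√(2/30) = 0.51 for 30 vs 30 (both stages).

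**6. After the fix.** Comparing patients within the same amount brings the expected gap to 0 in every scenario above, because race has no effect at a given amount by assumption. The documents give no outcome difference by stage, so the contribution of stage cannot be sized.

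**The case against.** The strongest reply is that this is a descriptive feasibility pilot. Section 5.1.2 asks for no power calculation and sets benchmarks on retention and survey completion. No test, causal claim or dose decision rests on the race and residence comparisons. That stands. It limits how much the point matters, but it does not make a contrast that mixes amount with race easier to read.

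Several further limits also stand:

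- A reader might infer that every drift in case mix becomes a race or rural effect. It does not. The race or residence mix itself must differ between amounts, and the amount must both change and affect the outcome. With an even mix, or if every cohort stays at $1000, the distortion is zero. Drift in characteristics unrelated to race or residence adds noise only.
- A reader might take 14 points as the expected size. That needs one cohort at each amount, which has probability about 0.10 under the stated rule and prior. The drift is itself assumed; nothing in the documents predicts it or its direction.
- Pooling across amounts is the natural reading of 5.1.3, but it is not stated in words. Nor does 5.1.1 say whether the 50% aims apply overall or per cohort.
- Variables measured before payment, such as sociodemographic data and baseline COST, cannot be affected by the amount.
- Greater baseline hardship in one group may be part of the disparity being described. Section 2 reports financial distress in 40% of Black and 23% of White patients. Adjusting for baseline COST therefore answers a different question, and its omission from the main comparison is not an error.
- The 9-point mean is smaller than one sampling SE, whether 16.4 or 11.6 points. That argues for showing intervals, not for leaving amount out.

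**Conclusion.** The point holds as an analysis improvement worth making. For outcomes measured during payment, the only planned comparison does not account for an assigned factor that the protocol expects to move unsuitability from 5% to 60%, and it has no interval. Under a moderate assumed drift with no true race effect, the mean spurious gap is about 9 points (95% range 5 to 14), and the sign reverses if the drift reverses. With a random mix and one cohort per amount it averages 0 with SD about 7 points.

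These sizes rest on the protocol's prior model, the 4.4.1.10 rule, equal Black and White numbers, and race mixes that the documents do not give. They apply to the suitability outcome; the documents do not quantify an amount effect on COST, AIM or IAM scores. The same mechanism applies to rural and urban residence. The documents do not support saying that the comparisons will be biased, only that the plan as written could not show whether they are.

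**What to change.** In 5.1.3:

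- Keep the crude Cohen's d or Cramer's V and label it descriptive.
- For outcomes measured during payment (COST, AIM, IAM and suitability), report beside it the race and residence differences adjusted for reimbursement amount and stage, each with a 95% CI.
- Add a table of race and residence by amount, so that readers can see whether the mix differed.
- If wanted, show a version also adjusted for baseline COST as a secondary result, stating that it addresses a different question.

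Amount, stage, race, residence and baseline COST are already recorded, so the cost is a few sentences and a little more analysis. The intervals will be wide (half-width of d about 0.5 for 30 vs 30 and 0.7 for 15 vs 15), which is useful information for planning the next study.

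Race and residence quotas within each cohort of 5 are not recommended. Six successive cohorts followed for 4 months take 6 × 4 = 24 months, already the whole two years in 4.2 before any accrual time.
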